Dose escalation decisions will be made in accordance with a 3+3 design modified to allow flexibility in the initial cohort size (decision rules noted in Table 1). Dose escalation will occur at the planned dose levels until the MTD is determined or until the highest dose level is tested. The MTD is defined as the highest dose level with an observed incidence of DLT in < 33% of subjects enrolled in a cohort dose level. At least 6 subjects will be treated at the MTD or highest tested dose.

Table 1. 3+3 Dose Level Decision Rules

#Subjects ^a	#Subjects with DLT	Decision
3-4	1	Enroll 2-3 additional subjects at same dose level
3-4	0	Escalate ^b
3-4	≥ 2	De-escalate ^c
6	1	Escalate ^b
6	≥ 2	De-escalate ^c

^a Subjects who are not DLT-evaluable (see Section 3.4) are excluded from the count of subjects

^b If final dose level has been reached, accrual will be suspended.

^c If 6 subjects already entered at next lower dose level, the estimated MTD has been established.

Part 2 – Dose Expansion:

In the Part 2 of the study up to 20 subjects with relapsed or refractory multiple myeloma will be treated. Subjects will be divided into the following 2 groups based on the status of prior treatment with CD38 targeting antibody (eg, Daratumumab):

- Group A will consist of subjects who had prior treatment with a CD38 targeting antibody (at least 10 subjects).
- Group B will consist of subjects who are naïve to CD38 targeting antibody treatment (approximately 10 subjects).

A body weight-based dosing will be evaluated in the Dose Expansion part of the study. Subjects will be treated with preliminary MTD identified from the Dose Exploration part of the study [REDACTED] adjusted for their body weight. Subjects with grade 2 thrombocytopenia at baseline (ie, platelet count < 75 to 50 x 10⁹/L) should be started at

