3.4 Replacement of Subjects

During dose exploration, subjects that are not DLT-evaluable will be replaced. A subject is not DLT-evaluable if the subject discontinues treatment for any reason other than a DLT prior to completing the first 28 days of AMG 224 treatment or does not receive 2 doses of AMG 224 during the 28-day DLT window. Additional subjects may be enrolled if Amgen’s medical monitor determines that the minimum required numbers of subjects with evaluable tissue samples have not been enrolled.

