- If a subject permanently ended the study treatment before completion of DLT evaluation period for a reason other than experiencing a DLT, then another subject will be recruited to replace this subject for the evaluation of the MTD.

Dose escalation will occur at the planned dose levels until the MTD is determined or until the highest dose level is tested. The MTD is defined as the highest dose level with an observed incidence of DLT in $< 33\%$ of subjects enrolled in a cohort dose level. At least 6 subjects will be treated at the MTD or highest tested dose.

A DLT will be defined as any of the events described under ([Section 6.2.1.6](#)), occurring in a subject during the DLT window, and regarded by the investigators and/or Amgen medical monitor to be related to AMG 224. The DLT window will be the initial 28 days of treatment with AMG 224. The DLT window may also be extended to assess events starting within the window in case the DLT definition is time dependent (neutropenia or thrombocytopenia, see below). Any adverse event occurring outside the DLT window that is determined by the investigator to be possibly related to the investigational product, which is seen more frequently or is more severe than expected or is persistent despite appropriate management, can be determined to be a DLT upon unanimous decision by the DLRT after review of the adverse event and all available safety data. The CTCAE version 4.0 will be used to assess the severity of toxicities/adverse events. The DLRT may request additional reviews or recommend modifying or suspending the study if safety concerns arise during the study. In the event that a need to modify or suspend the study is identified, this information will be communicated to investigators immediately, in accordance with Amgen procedures, and in compliance with prevailing guidance, including EMEA/CHMP/SWP/28367/07 (Guideline on strategies to identify and mitigate risks for first-in-human clinical trials with investigational medicinal products). Refer to [Section 10.3.2](#) for additional details regarding the DLRT.

Dose Exploration Stopping Rules

The DLRT may consider part 1 dose exploration complete if one of the following rules is met:

- The highest planned dose level is evaluated, MTD has not been defined and no DLTs occur at any dose level, in this case the maximum administrated dose (MAD) may be used for part 2.
- A total of 40 DLT-evaluable subjects have been enrolled.
- An MTD is identified.

Approved

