Any subject meeting the criteria for Hy's Law case (ie, severe drug-induced liver injury) will be considered a DLT. A Hy's Law case is defined as: AST or ALT values of $\geq 3x$ ULN AND with serum total bilirubin level (TBL) of $> 2x$ ULN without signs of cholestasis and with no other clear alternative reason to explain the observed liver-related laboratory abnormalities (see [Section 6.4](#) for hepatotoxicity management and [Appendix A](#) for further explanation of Hy's law case and Management of Hepatic Function).

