6.4.1 Criteria for Permanent Withholding of AMG 224 due to Potential Hepatotoxicity

AMG 224 should be permanently withheld and the subject should be followed according to the recommendations in [Appendix A](#) (Additional Safety Assessment Information) for possible drug-induced liver injury (DILI), if ALL of the criteria below are met:

Increased AST or ALT from the relevant baseline value as specified below:

Baseline AST or ALT value	AST or ALT elevation
< ULN	> 3x ULN

AND

TBIL > 2 x ULN or INR > 1.5

AND

No other cause for the combination of the above laboratory abnormalities is immediately apparent; important alternative causes for elevated AST/ALT and/or elevated TBIL values include, but are not limited to:

- Hepatobiliary tract disease
- Viral hepatitis (eg, Hepatitis A/B/C/D/E, Epstein-Barr Virus, Cytomegalovirus, Herpes Simplex Virus, Varicella, Toxoplasmosis, and Parvovirus)
- Right sided heart failure, hypotension or any cause of hypoxia to the liver causing ischemia
- Exposure to hepatotoxic agents/drugs including herbal and dietary supplements, plants, and mushrooms
- Heritable disorders causing impaired glucuronidation (eg, Gilbert's syndrome, Crigler-Najjar syndrome) and drugs that inhibit bilirubin glucuronidation (eg, indinavir, atazanavir)
- Alpha-one antitrypsin deficiency
- Alcoholic hepatitis

- Autoimmune hepatitis
- Wilson’s disease and hemochromatosis
- Nonalcoholic Steatohepatitis (NASH) or other “fatty liver disease”
- Non-hepatic causes (eg, rhabdomyolysis, hemolysis)

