6.4.3 Criteria for Rechallenge of AMG 224 After Potential Hepatotoxicity

The decision to rechallenge the subject should be discussed and agreed upon unanimously by the subject, Principal Investigator, and Amgen. Subjects who clearly meet the criteria for permanent discontinuation (ie, no definite alternative cause for the laboratory abnormalities was discovered) (as described in [Section 6.2.1.4](#)) should never be rechallenged. If signs or symptoms recur with rechallenge, then AMG 224 should be permanently discontinued.

Approved

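### In Part 1, some subjects permanently stopped under Protocol 6.4.1 through the INR limb alone meet no DLT criterion, so a suspected drug-induced liver injury goes uncounted

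*Protocol*

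**What the plan says.** **The stopping rule.** Protocol 6.4.1 requires permanent withholding when three things hold together. The first is "Increased AST or ALT from the relevant baseline value as specified below", where the table gives baseline below ULN and a rise above 3 times ULN. The second is "TBIL > 2 x ULN or INR > 1.5". The third is that no other cause is immediately apparent. Section 6.4.3 bars rechallenge for subjects who clearly meet the permanent criteria, that is, where "no definite alternative cause for the laboratory abnormalities was discovered".

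**The DLT definition.** Protocol 6.2.1.6 states: "Any subject meeting the criteria for Hy's Law case (ie, severe drug-induced liver injury) will be considered a DLT". Its Hy's Law case needs AST or ALT at least 3 times ULN and bilirubin above 2 times ULN. The other liver criteria are:
- AST/ALT above 8 times ULN
- AST/ALT between 5 and 8 times ULN with a duration or monitoring condition
- AST/ALT above 3 times ULN with signs or symptoms of hepatitis
- bilirubin above 3 times ULN

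The general rule adds Grade 3 or higher non-hematological events. SAP section 5 repeats these liver criteria. Neither document has an INR criterion.

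**Evaluability.** Under Protocol 3.4 and SAP 6.3, a subject is not DLT-evaluable if treatment stops before day 28 for a non-DLT reason, or if the subject "does not receive 2 doses of AMG 224 during the 28-day DLT window". Table 1, footnote a: "Subjects who are not DLT-evaluable (see Section 3.4) are excluded from the count of subjects". Protocol 6.2.1.2 recruits a replacement: "If a subject permanently ended the study treatment before completion of DLT evaluation period for a reason other than experiencing a DLT".

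**The concern.** The liver bullets in the DLT list match the AST/ALT and bilirubin criteria of 6.4.2, which is the conditional-withholding rule. So events that may allow rechallenge are DLTs, while part of the more serious permanent rule is not. The documents do not explain the difference.

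Protocol 2.3 names hepatotoxicity as one of two anticipated toxicities, and DLT incidence is a primary endpoint. A permanent stop for suspected drug-induced liver injury should not be handled like an unrelated dropout, or recorded as a tolerated course. The error runs in one direction, toward understating toxicity. It reaches both the 3+3 count and the toxicity probability interval (TPI) model.

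**Working it through.** **1. Which subjects fall through.** Criteria applied case by case, with baseline AST/ALT below ULN and no other cause apparent:

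| AST/ALT (x ULN) | TBIL (x ULN) | INR | Hepatitis symptoms | 6.4.1 stop | Listed DLT |
|---|---|---|---|---|---|
| 4 | 1 | 1.6 | no | yes | **no** |
| 4 | 2.0 | 1.8 | no | yes | **no** |
| 4 | 1 | 1.6 | yes | yes | yes |
| 9 | 1 | 1.6 | no | yes | yes |
| 4 | 2.5 | 1.0 | no | yes | yes (Hy's Law) |

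The first two rows are the gap, provided nothing reaches Grade 3. The CTCAE cut-offs are not in the documents, so that proviso is an assumption.

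**2. What happens to such a subject.**
- Stop before day 28, or fewer than 2 doses: not evaluable, replaced, absent from Table 1 and from the TPI data.
- Both doses given and the stop decided after day 28: evaluable, counted as no DLT.

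**3. The plan's own figures** (Protocol 10.2). P(at least one DLT) = 1 - (1-p)^n. For n = 3 this gives 27.1% at p = 0.10 and 69.9% at p = 0.33. For n = 6 it gives 46.9% and 91.0%. The stated 27 to 70% and 47 to 91% reproduce.

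**4. Effect on the 3+3.** Let P be the true rate with these cases counted and q their frequency. The documents give no q, so 0.5% to 2% is assumed. For a cohort starting with 3, P(escalate) = (1-p)^3 + 3p(1-p)^5. If the cases are dropped and replaced, the counted rate is p = (P-q)/(1-q).

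| P | Cases counted | q = 0.5% | q = 1% | q = 2% | Excess, points |
|---|---|---|---|---|---|
| 0.10 | 90.6% | 91.4% | 92.1% | 93.5% | 0.7 to 2.8 |
| 0.20 | 70.9% | 71.7% | 72.6% | 74.4% | 0.9 to 3.5 |
| 0.33 | 43.4% | 44.1% | 44.8% | 46.1% | 0.7 to 2.7 |

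If the cases instead stay in as non-DLTs, the counted rate is P - q. At P = 0.20 and q = 2% that is 0.18, and P(escalate) = 0.82^3 + 3(0.18)(0.82^5) = 0.551 + 0.200 = 75.2%, an excess of 4.3 points.

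Among about 40 Part 1 subjects, the expected number of cases is 40q = 0.2 to 0.8. P(at least one) = 1 - (1-q)^40 = 18% to 55%.

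**5. Effect on the TPI model.** The inputs are the two-parameter logistic model and prior in SAP Appendix A (means 0.0536 and -0.1469, SDs 1.685 and 1.001, correlation -0.216). The redacted doses are assumed to be eight levels from 30 to 300 mg, spaced geometrically or equally, with the maximum planned dose at 300 mg and 0/3 at each lower level. The model was integrated on a grid. Adding one excluded case moves the data at the dose from 1/6 to 2/7:

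| Spacing, dose | Mean DLT rate | P(rate > 0.35) |
|---|---|---|
| Geometric, Cohort 7 | 13.5% to 19.7% | 3% to 9% |
| Geometric, Cohort 8 | 16.2% to 23.0% | 6% to 16% |
| Equal, Cohort 7 | 13.0% to 18.7% | 2% to 7% |
| Equal, Cohort 8 | 13.5% to 19.3% | 3% to 9% |

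All stay under the 0.25 limit at that dose. With 2/6, where the case is one of the six, P(rate > 0.35) is 10% to 22%, still under the limit.

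Applying the full selection rule, 1/6 to 2/7 leaves the chosen dose unchanged. The equal-spacing Cohort 7 layout is a borderline result, because the untested Cohort 8 has an overdose probability of about 0.25. With 2/6 in that layout, Cohort 8 rises to about 0.29 and the choice moves down to Cohort 7. The other three layouts do not change.

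**The case against.** **The case is narrow.** Many INR-limb subjects are DLTs by another route: symptoms such as fever, nausea or rash, a higher transaminase level, or any Grade 3 event. A reader might infer that every INR-limb stop escapes the DLT count. The documents do not support that, and the point covers only the residual group.

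**Exclusion is not automatic.** A subject with both doses and a stop decided after day 28 remains evaluable. This stands, but that subject is then counted as having no DLT, so the downward bias remains.

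**The cross-reference.** Section 6.2.1.6 sends the reader to Appendix A for explanation of a Hy's Law case, and Appendix A mentions INR. That text governs reporting and follow-up. The definition in 6.2.1.6 itself is explicit and uses bilirubin only.

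**Oversight.** The event is reported as serious within 24 hours. The dose level review team sees all data and may stop enrollment or repeat or expand a cohort. A reader might infer that the toxicity would go unseen, and that would be wrong. What the team lacks is a stated power to name an in-window event as a DLT. The power given in 6.2.1.2 is for "Any adverse event occurring outside the DLT window that is determined by the investigator". Discretion over dosing does not put the subject into the TPI data.

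**Design choice.** DLT and withholding rules need not coincide. For example, ALP above 8 times ULN leads to withholding under 6.4.2 but is not a listed DLT. This is fair in general. It is weaker for a permanent stop with no alternative cause.

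**Little is still open.** Protocol 2.4.2 treats the preliminary MTD as identified, and the Amendment 2 rationale reports no DLT up to Cohort 6. This stands, and it limits the practical effect. Some of these subjects would be lost anyway, since AST/ALT above 3 times ULN holds dosing and an in-window delay over 7 days means replacement (6.2.1.5).

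**The frequency is unsourced.** At 0.05% to 0.2%, equally unsourced, the excess is about 0.07 to 0.35 points.

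**Conclusion.** The gap is in the text and the point holds as a minor one, worth correcting. A suspected drug-induced liver injury that ends treatment in Part 1 can go uncounted, either by exclusion and replacement or by being recorded as no DLT. The DLT rate is biased slightly down.

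The live effect is on the reported DLT incidence and on the TPI fits, after 5 expansion subjects and at the end. Most escalation decisions appear to have been taken already.

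Two stronger readings do not hold. One case does not by itself turn 1/6 into 2/6, because that needs another DLT already in the cohort. With no other DLT, one case leads to expansion of the cohort and, if no more follow, 1/6, which still escalates. Nor do the documents show that the selected dose is wrong. In the assumed layouts one case shifted the estimate but usually left the choice unchanged.

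The sizes rest on an assumed frequency, assumed dose spacing, a 300 mg maximum, and such events falling below Grade 3.

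**What to change.** 1. **Protocol 6.2.1.6 and SAP section 5.** Keep the Hy's Law sentence. Add that a subject who meets the 6.4.1 permanent-withholding criteria within the DLT window, including through INR above 1.5, counts as a DLT unless workup establishes another cause for the combined abnormalities. Say that anticoagulant use (exclusion 212 allows it case by case) or a baseline INR above 1.5 (possible under inclusion 109 where the laboratory ULN exceeds 1.0) may explain the INR, but does not by itself excuse an unexplained transaminase rise. Tying the clause to 6.4.1 leaves out subjects who enter with AST/ALT above ULN, as inclusion 111 permits.
2. **Protocol 3.4 and SAP 6.3.** State that any subject with a DLT is DLT-evaluable and is not replaced, whatever the number of doses received. Read literally, the two-dose condition would exclude any DLT that occurs before dose 2, so the sentence should cover all DLTs.
3. **TPI fits.** Apply the same definition to all Part 1 subjects, using the INR results already collected under the schedule of assessments.

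The cost is one sentence or two in each definition and a short retrospective check. The 6.4.1 rule does not change and no new data are needed. The downsides are a slightly higher DLT count, a slightly more conservative dose estimate, and a re-check of Part 1 DLT status after the expansion dose was chosen. That re-check should be disclosed.

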6.3 Management of Adverse Events

6.3.1 Management of Thrombocytopenia

Increased monitoring should be implemented in subjects whose platelet counts are $< 100 \times 10^9/L$ and subjects on anti-coagulant or anti-platelet treatment. Hematology panels should be repeated on days 5, 6, or 7, or as clinically indicated, following each dose, if platelet counts are $< 75 \times 10^9/L$, until platelet counts are $\geq 75 \times 10^9/L$ (Grade 1).

Subjects should not receive anti-coagulant therapy or anti-platelet therapy while treated with AMG 224 unless in the opinion of the investigator and in consultation with Amgen's medical monitor the use of these agents is medically necessary. Use caution with these agents and consider additional monitoring as described above when concomitant of these agents is medically necessary.

Details of dose modification based on pre-dose platelet count are described in [Table 4](#).

The investigator should notify Amgen immediately before administration of the lower dose of AMG 224.

Subjects who have been dose-reduced will have an option to receive the higher dose (ie Dose Level -1 or Dose Level 1 as outlined in [Table 3, Section 6.2.1.5](#)) at the next planned cycle if the adverse event resolves \leq grade 1 or baseline and the reintroduction of AMG 224 at the higher dose is deemed safe by the Investigator. The investigator should notify Amgen immediately before administration of the higher dose of AMG 224.

Treatment for thrombocytopenia should be initiated per standard of care as clinically indicated. Any subject who experiences a Grade 3 or 4 thrombocytopenia that cannot be managed per standard of care, will be permanently discontinued from AMG 224 treatment.

Table 4. Dosing Guideline Based on Platelet Count After 2nd Cycle

Grade of Platelet Count Decrease	Withhold Dose	Previous dose	Previous dose	Dose Discontinuation
Grade 0 or 1 (PLT LLN to $\geq 75 \times 10^9/L$)	No	Continue to administer AMG 224 at Dose Level 1 (██████████ Q3W)	Escalate to one higher Dose Level (██████████ Q3W)	N/A
Grade 2 (PLT 75 to $\geq 50 \times 10^9/L$)	No	Continue to administer AMG 224 at Dose Level 1 (██████████ Q3W)	Continue to administer AMG 224 at the same dose level	N/A
Grade 3 (PLT <50 to $\geq 25 \times 10^9/L$)	Yes, don't administer AMG 224 until platelet count recovers to \leq Grade 2 ($\geq 50K$)	Upon recovery, administer AMG 224 at Dose Level 1 (██████████ Q3W)	Upon recovery, administer AMG 224 at the same dose level	Yes, if grade 3 platelet count decrease did not recover to at least grade 2
Grade 4 (PLT $< 25 \times 10^9/L$) and last ≤ 7 days	Yes, don't administer AMG 224 until platelet count recovers to \leq Grade 2 ($\geq 50K$)	Upon recovery, administer AMG 224 at Dose Level -1 (██████████ Q3W) if deemed safe by the investigator	Upon recovery, administer AMG 224 at one lower Dose Level (minimum ██████████ Q3W) if deemed safe by the investigator	Yes, if grade 4 platelet count decrease did not recover to at least grade 2 OR subsequent drops in platelet count to Grade 4 after dose reduction

Approved

Table 4. Dosing Guideline Based on Platelet Count After 2nd Cycle

Grade of Platelet Count Decrease	Withhold Dose	Previous dose	Previous dose	Dose Discontinuation
Grade 3 or 4 PLT count decreased associated with < grade 2 bleeding	Yes, don't administer AMG 224 until platelet count recovers to ≤ Grade 2 (≥ 50K) and bleeding is controlled	Upon recovery, administer AMG 224 at Dose Level -1 (██████████) Q3W) if deemed safe by the investigator	Upon recovery, administer AMG 224 at one lower Dose Level (minimum ██████████ Q3W) if deemed safe by the investigator	Yes, if grade 3 or 4 platelet count decrease did not recover to at least grade 2 and bleeding is not controlled OR subsequent episode of Grade 3 or 4 thrombocytopenia associated with < grade 2 bleeding
Grade 4 (PLT < 25 10 ⁹ /L) and last > 7 days or Grade 3 or 4 (PLT < 50 10 ⁹ /L) with ≥G2 bleeding	N/A	N/A	N/A	Yes

Page 2 of 2

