During the DLT-window, if the dosing is delayed for more than 7 days the subject will be removed from the study and will be replaced. After DLT-window, if the dosing is delayed for ≤ 3 weeks, the subject should resume the treatment as soon as possible if deemed safe by the investigator. The investigator should inform the Amgen Clinical team as soon as the unexpected dosing interruption occurs. If the dosing of AMG 224 is delayed more than 3 weeks (missing 1 cycle) due to treatment-related adverse events, the subject will be removed from the study. If the dosing delay occurred under conditions other than those associated with AMG 224 related toxicities, the case will be reviewed by Amgen medical monitor to determine whether the subject will be allowed to resume AMG 224 treatment.

Rules for Withholding or Restarting

AMG 224 should be withheld for any of the following:

- Suspected DLT (including AE that meet DLT definition outside DLT window)
- Grade 3 thrombocytopenia (follow the thrombocytopenia management in [Section 6.3.1](#))
- Aspartate aminotransferase (AST) or alanine aminotransferase (ALT) greater than 3x ULN or total bilirubin greater than 1.5x ULN

AMG 224 dosing can be resumed if the toxicities resolve to grade ≤ 1 or return to subjects' baseline values. The restarting of therapy should be deemed safe by the investigators and Amgen's medical monitor.

Rules for Permanent Discontinuation

Subjects will permanently discontinue from the investigational product if:

- Subjects experience adverse events meeting the DLT criteria at any time. Subjects will be followed until the DLT is resolved, returns to baseline value or is considered stable. Subjects will be withdrawn from AMG 224 treatment and will be treated as deemed appropriate by the investigator or treating physician. Except for:
 - Subjects showing evidence of response or subjects who in the opinion of the investigator may be responding to AMG 224, may have the option to continue therapy once the adverse events recover to baseline or Grade 1 and the re-introduction of AMG 224 is deemed safe by the investigator, Amgen's medical monitor, and Global Safety Officer. The subject should

restart at a reduced dose (see [Section 6.2.1.4](#)) subsection Dose Adjustments).

- Intolerability of the study treatment
- The dosing is delayed > 3 weeks due to AMG 224-related adverse events
- Disease progression according to IMWG response criteria
- Clinical significant deterioration of health status

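### Protocol Table 4: the row for Grade 3 or 4 platelets with bleeding below Grade 2 stops treatment on a weaker condition than the rows without bleeding, and it collides with the discontinuation row for Grade 4 lasting more than 7 days

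*Protocol*

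**What the plan says.** Table 4 in Protocol Section 6.3.1 applies after the second cycle and uses the expansion dose levels of Table 3. Four of its rows matter here.

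- **Plain Grade 3 row.** Withhold until platelets are at least 50 x 10^9/L, then: "Upon recovery, administer AMG 224 at the same dose level". Discontinue if platelets do not recover to Grade 2. Bleeding is not mentioned.
- **Plain Grade 4 row, 7 days or less.** Withhold to the same threshold, then go one level lower if the investigator judges it safe. Discontinue if platelets do not recover, or if Grade 4 recurs after the reduction.
- **Bleeding row.** Entry: "Grade 3 or 4 PLT count decreased associated with < grade 2 bleeding". The withhold cell asks for platelet recovery to the same threshold ("50K) and bleeding is controlled"). The dose cell reads "Upon recovery, administer AMG 224 at one lower Dose Level", subject to the investigator's safety judgement. The discontinuation cell reads "Yes, if grade 3 or 4 platelet count decrease did not recover to at least grade 2 and bleeding is not controlled", or a repeat episode.
- **Last row.** Entry covers Grade 4 ("and last > 7 days or Grade 3 or 4" with Grade 2 or worse bleeding). The action is discontinuation; the withhold and dose cells are marked not applicable.

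Section 6.2.1.5 requires permanent discontinuation for any event meeting DLT criteria, whenever it occurs, and Section 6.2.1.6 lists Grade 4 thrombocytopenia beyond 7 days among those criteria. Section 6.2.1.5 then makes an exception for responders: "subjects who in the opinion of the investigator may be responding to AMG 224, may have the option to continue therapy", but only "once the adverse events recover to baseline or Grade 1 and the re-introduction of AMG 224 is deemed safe by the investigator", the medical monitor and the Global Safety Officer, and at a reduced dose.

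**The concern.** Thrombocytopenia is the primary safety concern named in Section 2.4.2, and the Amendment 4 rationale gives subject safety as the reason for this dosing schedule. A table of this kind should give each clinical state one action, and it should not become more lenient when bleeding is added to a low platelet count. The bleeding row falls short on both counts. Its stop condition is not the complement of its resume condition, and its entry criterion admits subjects whom the last row takes off treatment. At stake is a hold that the table does not end, and uncertainty over whether, and at what platelet count, a possible responder with prolonged Grade 4 may be dosed again.

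**Working it through.** The plan gives no figure to reproduce, so the check is logical. I read bleeding below Grade 2 as Grade 1, consider first episodes, and assume throughout that a subject who bled is governed by the bleeding row rather than by a plain row.

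**Step 1: stop against resume.** Let R mean platelets recovered to at least 50 x 10^9/L and C mean bleeding controlled. The bleeding row resumes on (R and C) and discontinues on (not R and not C). The complement of (R and C) is (not R or not C), which is a wider condition.

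| Platelets | Bleeding | Bleeding row as written | Plain row, subject who never bled |
|---|---|---|---|
| recovered | controlled | resume one level lower | resume (Grade 3: same level; Grade 4: one lower) |
| recovered | not controlled | neither resume nor discontinue | not applicable |
| not recovered | controlled | neither resume nor discontinue | discontinue |
| not recovered | not controlled | discontinue | not applicable |

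Two of the four combinations have no end action in the row. The third line is the telling one: with the same unrecovered platelets, the subject who never bled is discontinued and the subject who bled is only held.

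**Step 2: what ends the hold.** The exits lie outside the row. Section 6.2.1.5 discontinues for a drug-related delay beyond 3 weeks and sends other delays to the medical monitor. It also bars rechallenge after a related Grade 3 event that has not returned to baseline or Grade 1 within 4 weeks. The text above Table 4 discontinues when standard care cannot manage Grade 3 or 4 thrombocytopenia.

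**Step 3: Grade 4 beyond 7 days with a Grade 1 bleed.** This subject meets the entry criteria of both the bleeding row and the last row, and neither Table 4 nor the text of Section 6.3.1 says which governs.

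- Last row: discontinue.
- Bleeding row, after recovery and control: one level lower at 50 x 10^9/L or above, if the investigator judges it safe.
- Section 6.2.1.5, non-responder: discontinue, because a DLT criterion is met. This agrees with the last row and settles the case.
- Section 6.2.1.5, actual or possible responder: reduced dose only after return to baseline or Grade 1 (75 x 10^9/L or above), with the medical monitor and Global Safety Officer also agreeing.

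For responders three rules remain. The two that allow re-dosing differ by 75 - 50 = 25 x 10^9/L in the platelet threshold, and in who must agree. The threshold gap narrows for a subject who entered with Grade 2 platelets, since baseline then lies between 50 and 75.

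**Step 4: Grade 3 with a controlled Grade 1 bleed.** The plain Grade 3 row gives the same dose and the bleeding row one level lower. If the plain row governed, the mention of Grade 3 in the bleeding row would have no effect, so the specific row must prevail. What is missing is a label on the plain row.

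**The case against.** The strongest reply is that the table is a severity ladder that clinicians will read sensibly. No dose is given while either problem persists, so the faulty stop condition exposes nobody to drug. Restart must be judged safe by the investigators and the medical monitor, and the sponsor is told before a lower dose is given, which limits divergence between sites. On prolonged Grade 4, the last row takes effect once 7 days are exceeded, normally before platelets can reach 50 x 10^9/L, so the bleeding row's recovery clause concerns someone already off treatment. The tension between the responder exception and the last row also exists without any bleeding.

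Most of this stands, and it keeps the severity low. It does not make the discontinuation cell right: the row that adds bleeding still has the weaker stop. The timing argument does not close the responder case, because Section 6.2.1.5 expressly reopens treatment for those subjects and the bleeding row offers a route with a lower threshold.

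Three stronger readings are tempting and are not supported. A reader might infer an indefinite hold; the general rules in Step 2 bound it. A reader might take the Grade 3 overlap as a true contradiction in dose; the specific-row reading resolves it. A reader might infer that prolonged Grade 4 generally permits re-dosing; for non-responders Sections 6.2.1.5 and 6.2.1.6 rule that out.

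**Conclusion.** The bleeding row is wrong as written in two respects: its stop condition is looser than that of the plain rows, and without a Grade 4 duration limit it conflicts with the last row, a conflict that remains open for actual or possible responders only. Severity is low. The rows apply after the second cycle and to expansion dose levels, so at most 20 subjects could be affected; the documents give no basis for estimating how many would be. The default is to withhold. The DLT and MTD analysis does not change, because its primary form counts only events inside the 28-day window.

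The conclusion rests on reading bleeding below Grade 2 as Grade 1 and on letting the bleeding row govern subjects who bled. If the plain rows applied to them as well, platelet non-recovery alone would discontinue and that gap would close, but the Grade 3 dose conflict of Step 4 would then be real. Neither reading leaves the table consistent.

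**What to change.** Four wording changes to Section 6.3.1 and Table 4:

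1. In the bleeding row's discontinuation cell, replace *and* with *or*, judged at the existing 3-week delay limit. Subjects are then held for up to 3 weeks and stop only if either condition is still unmet, so a slowly resolving Grade 1 bleed does not force an immediate stop.
2. Limit the bleeding row to Grade 3, or Grade 4 of 7 days or less, with Grade 1 bleeding. The last row then governs all Grade 4 beyond 7 days.
3. Add *without bleeding* to the plain Grade 3 and Grade 4 (7 days or less) rows. This supplies the missing label and also removes their overlap with the last row when bleeding is Grade 2 or worse.
4. State whether the responder exception in Section 6.2.1.5 overrides the last row. If it does, its recovery threshold and approvals apply.

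The cost is a text edit in the next amendment, with no extra data, visits or subjects. The downside is that a few subjects with persistent Grade 1 bleeding would stop under the table rather than after case review. That concerns mainly holds not attributed to AMG 224, since related delays beyond 3 weeks already end treatment.
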